6.3 Instructions for Evaluations

All clinical and laboratory information required by this protocol is to be present in the source documents. Sites must refer to the Source Document Guidelines on the DAIDS Web site for information about what must be included in the source document: http://www.niaid.nih.gov/labsandresources/resources/daidsclinrsrch/documents/sourced ocappndx.pdf.

All stated evaluations are to be recorded on the CRF and keyed into the database unless otherwise specified. This includes events that meet the International Conference on Harmonisation (ICH) definitions for a SAE:

- Results in death
- Life-threatening
- Requires inpatient hospitalization or prolongation of existing hospitalization
- Results in persistent or significant disability/incapacity
- Congenital anomaly/birth defect
- Other important medical event (may not be immediately life-threatening or result in death or hospitalization but may jeopardize the patient or may require intervention to prevent one of the events listed above).

To grade diagnoses, signs and symptoms, and laboratory results, sites must refer to the DAIDS Table for Grading the Severity of Adult and Pediatric Adverse Events (DAIDS AE Grading Table), Version **2**.0, **November 2014**, which can be found on the DAIDS RSC Web site: http://rsc.tech-res.com/safetyandpharmacovigilance/.

6.3.1 Documentation of HIV-1

Section 4.1.1 specifies assay requirements for HIV-1 documentation. HIV-1 documentation is not recorded on the CRF.

6.3.2 Medical History

The medical history must include all diagnoses identified by the ACTG criteria for clinical events and other diagnoses. In addition to reporting all diagnoses within the past 30 days, the following diagnoses should be reported regardless of when the diagnosis was made.

- AIDS-defining conditions
- Bone fractures (verbal history accepted)
- Coronary heart disease
- Cancer (exclusive of basal/squamous cell skin cancer)
- Diabetes

- Tuberculosis
- Chronic **or acute** HCV
- Chronic or acute HBV
- HIV encephalopathy
- HIV wasting
- Esophageal candidiasis
- Pneumocystis pneumonia without dissemination

Any allergies to any medications and their formulations must also be documented.

6.3.3 Medication History

A medication history must be present, including start and stop dates. The table below lists the medications that must be included in the history.

Medication Category	Complete History or Timeframe	Record on CRFs
ART	Complete history (estimated dates if the exact dates cannot be obtained)	Yes
Immune-based therapy	Complete history (estimated dates if the exact dates cannot be obtained)	Yes
HIV-1-related vaccines	Complete history	Yes
Prescription drugs for treatment of opportunistic infections	Within 30 days prior to study entry	Yes
Prescription drugs for prophylaxis of opportunistic infections	Within 30 days prior to study entry	Yes
Prescription drugs: All including statins, anticoagulation therapy, NSAIDS, anti-inflammatory drugs not considered immune based therapy	Within 30 days prior to study entry	Yes
Alternative therapies	Within 30 days prior to study entry	Yes
Dietary supplements	Within 30 days prior to study entry	Yes
Aspirin use	Documentation of any aspirin use over a period of more than 5 days in any given week, taken within 30 days prior to study entry	Yes

6.3.4 Physical Examinations

Complete Physical Exam

A complete physical examination is to include at a minimum an examination of the skin, head, mouth, and neck; auscultation of the chest; cardiac exam; abdominal exam; examination of the lower extremities for edema; and Karnofsky performance score. The complete physical exam will also include signs and symptoms, diagnoses, and vital signs (temperature, pulse, respiration rate, and blood pressure).

Targeted Physical Exam

A targeted physical examination is to include vital signs (temperature, pulse, respiration rate, and blood pressure) and is to be driven by any previously identified diagnoses or new signs or symptoms that the **participant** has experienced within 30 days prior to entry or since the last visit.

6.3.5 Clinical Assessments

Height

Height (in cm) will be measured at the entry visit.

Weight

Weight (in kg) will be measured at screening, entry and at all subsequent study visits.

Signs and Symptoms

At entry, all grades that occurred 30 days before entry must be recorded; postentry, only signs and symptoms Grade \geq 2 must be recorded except record all non-traumatic bruising regardless of grade. All Grade 3 or higher sign/symptom, any sign/symptom regardless of grade that led to a change in treatment, or that met ICH, EAE, or SAE guidelines, are defined by the protocol as reportable events that will require more detailed event reporting and must be reported on the CRF within 2 business days.

Diagnoses

At entry and on-study visits, record all diagnoses identified by the ACTG criteria and any of the following targeted diagnoses occurring since the last study visit:

• New onset seizures; or physician diagnosed CNS abnormality.

Post entry diagnoses must be reported on the CRF within 2 business days.

6.3.6 Concomitant Medications

Record in source documents and CRFs additions or discontinuations of any prescription medications and any medication or supplement included in the precautionary medication list (See PSWP). Record on the **source documents and** CRFs use of aspirin (chronic use only, defined as daily aspirin use over a period of more than 5 days in any given week) since the last study visit, including actual or estimated start dates and stop dates.

6.3.7 Study Treatment Modifications

Record all study drug modifications, including initial doses, **participant**-initiated and/or protocol-mandated modifications, inadvertent and deliberate interruptions, and permanent discontinuation of treatment at each visit. **Participant** missing

greater than 3 doses of study drug per week for two or more weeks results in a study treatment discontinuation and should be recorded on the CRF. The protocol core team ([contact]) must be notified of any permanent discontinuation of study drug.

6.3.8 ART Modifications

Record all modifications, including initial doses, **participant**-initiated and/or protocol-mandated modifications, inadvertent and deliberate interruption of 7 days or more and permanent discontinuation.

Arm A **participants** who change or discontinue ART must prematurely discontinue study treatment and be followed on study/off study treatment. Refer to protocol section 6.2.4 for premature treatment discontinuation evaluations.

6.3.9 Laboratory Evaluations

All laboratory evaluations at entry and week 5 study visit must be collected in a fasting state (8-hour fast with exception of water and medications). If **participants** are in a non-fasting state at the time of the study visit, they should return to the clinic within 72 hours for a fasting blood draw.

- At screening and entry all laboratory values must be recorded.
- For post-entry assessments, record all Grade ≥ 2 laboratory values, except for estimated CrCl, creatinine, AST (SGOT), ALT (SGPT), ANC, hemoglobin, and platelet count. These values should be recorded at every visit regardless of grade.
- All grade 3 or higher laboratory values, any laboratory value that led to a change in treatment or that met ICH, EAE, or SAE guidelines are defined by the protocol as reportable events that will require more detailed event reporting and must be reported on the CRF within 2 business days.

Although specific virologic and immunologic assays are described below, newer technology may preclude the utility of these assays and, therefore, this protocol will allow for the more advanced assays to be performed instead.

Hematology

Hemoglobin, hematocrit, red blood cells (RBC), mean corpuscular volume (MCV), white blood cells (WBC), differential WBC, absolute neutrophil count (ANC), platelets.

Liver Function Tests

AST (SGOT), ALT (SGPT), alkaline phosphatase, indirect bilirubin, direct bilirubin, and total bilirubin.

NOTE: Indirect bilirubin may be calculated from the total and direct bilirubin values.

Blood Chemistries

Electrolytes (sodium, potassium, chloride, bicarbonate), glucose, creatinine, blood urea nitrogen (BUN) and CrCl as estimated by the Cockcroft-Gault equation.

NOTE: A calculator for estimating the CrCl can be found at: https://www.fstrf.org/apps/cfmx/apps/common/Portal/index.cfm?event=postLogin.

Fasting Lipid Panel

Cholesterol, triglyceride, high-density lipoprotein (HDL), low-density lipoprotein (LDL). If the LDL cannot be calculated due to elevated triglyceride levels, a direct LDL should be measured.

Pregnancy Testing

For women with reproductive potential: Serum or urine β -HCG (urine test must have a sensitivity of 25 mIU/mL).

6.3.10 Nadir CD4+ T cell Count

The **participant**'s prior nadir CD4+ T cell count (absolute value and date) should be documented when possible with a copy of the nadir CD4+ T cell count report. If this documentation is not available, then **participant** recollection will suffice. For **participants** who do not know the exact nadir value and for whom there is no source documentation, then recall of the categorical nadir (e.g., < 50, < 100, < 200 cells/mm³) will suffice.

6.3.11 Documentation of Pre-ART CD4+ T cell Count

Record on the CRF the documented date and level of the **participant's** pre-ART CD4+ T cell count that was obtained most immediately prior to a **participant's** initiating ART. If documentation is not available, then **participant** recollection will suffice.

6.3.12 Immunologic Studies

CD4+/CD8+

At screening, pre-entry and for all on-study evaluations obtain absolute CD4+/CD8+ count and percentages from a laboratory that possesses a CLIA certification or equivalent and is certified for protocol testing by the DAIDS Immunology Quality Assurance (IQA) Program. Note only one CD4+/CD8+ value is needed if the screening and pre-entry visits are combined.

Because of the diurnal variation in biomarkers that may be measured as part of the study (e.g., CD4+ and CD8+ T cell counts and other biomarkers that may be measured on stored samples), blood draws for individual **participants** should be performed consistently in either the morning or the afternoon throughout the study, if possible.

6.3.13 Stored PBMCs for Other Immunologic Studies

PBMCs will be collected and stored at the indicated visits per section 6.1 (see Laboratory Processing Chart [LPC] for more information) for potential comparative assessment of:

- At specified time points, cellular (macrophage/monocytes and lymphocytes) markers of immune activation and inflammation in the peripheral blood including but not limited to HLA-DR, CD16+, CD38, CD56, CD69, and CD14+CD16+ monocyte levels will be determined using flow cytometry and using stored specimens at the end of the study.
- Lymphocyte markers of immune activation in the peripheral blood including but not limited to HLA-DR, CD38, CD69, and CD14+/CD16+ monocyte levels using microarray panels for both mRNA and protein expression.
- Macrophage/monocyte markers of immune activation and inflammation in the peripheral blood including but not limited to HLA-DR, CD38, CD69, and CD14+CD16+ monocyte levels using microarray panels for both mRNA and protein expression.
- 6.3.14 Stored Plasma Soluble Markers

Plasma for stored soluble markers will be collected and stored at the indicated visits per section 6.1 (see LPC for more information) for comparative assessment of:

- Soluble markers of immune activation and inflammation in the peripheral blood including but not limited to sCD14, TNF-α, IL-1α, IL-18, IL-1β, mCSF, and neopterin will be determined using enzyme-linked immunoassay using stored specimens at the end of the study.
- Soluble markers of immune activation and inflammation in the peripheral blood including but not limited to sCD14, TNF-α, IL-1α, IL-1β, mCSF, and neopterin using microarray panels.
- 6.3.15 Stored Plasma Soluble Marker: IL-6

Plasma for stored soluble marker IL-6 will be collected and stored at the indicated visits per section 6.1.

6.3.16 Documentation of Pre-ART HIV-1 RNA

Record on the CRF the documented date and level of the **participant's** pre-ART viral load that was obtained immediately prior to a **participant's** initiating ART. If documentation is not available, then **participant** recollection will suffice.

A5336 FINAL Version 2.0 05/21/15

6.3.17 Virologic Studies

Plasma HIV-1 RNA

Screening HIV-1 RNA must be performed within 30 days prior to study entry. All HIV-1 RNA determinations must be done using an FDA-approved assay with a lower limit of quantification < 50 copies/mL (eg, < 40 copies/mL obtained by the Abbott real-time assay or < 20 copies/mL by the Roche Taqman v2.0 assay) performed by a laboratory that possesses a CLIA certification or equivalent. Eligibility will be determined based on the screening value.

After the screening visit, HIV-1 RNA quantification assay will be performed at the protocol-designated laboratory. See the LPC for processing, shipping, and storage information.

6.3.18 Stored Plasma for HIV-1 RNA Single Copy Assay (SCA)

Plasma will be obtained and stored for determination of plasma HIV-1 RNA by SCA at the indicated visits per section 6.1. This assay will be performed if significant changes in the immunologic markers are observed and/or if there are advances in the field that might provide further rationale for assessing the virologic endpoints in the absence of achieving the desired immunologic outcomes. See the LPC for details on processing plasma samples for the SCA test.

6.3.19 Stored PBMC Reservoir Assays

Samples will be collected and stored as indicated in section 6.1 for potential comparative assessments of change in HIV-1 reservoir size as measured by:

- a. Total and integrated HIV-1 DNA
- b. HIV-1 cell-associated RNA
- c. 2 LTR circles

Reservoir assays will be performed if significant changes in the immunologic markers are observed and/or if there are advances in the field that might provide further rationale for assessing the virologic endpoints in the absence of achieving the desired immunologic outcomes.

6.3.20 Stored Plasma/PBMC

Stored Plasma/PBMC will be collected and stored as indicated in section 6.1 for future HIV-1 related studies and shipped according to the A5336 LPC.

6.3.21 Stored Oral Swabs Collection

Oral swabs will be collected as indicated in section 6.1 to measure levels of HHV DNA. It is recommended that participants abstain from drinking coffee 1 hour prior to collection. Samples will be stored and shipped according to the A5336 LPC.

6.3.22 Plasma PK Sample Collection for Arm A Participants

Samples will be collected as indicated in section 6.1 for assessment of the PK of ruxolitinib and ARV medicines. Apart from arriving at the clinic in a fasted state, participants may eat and drink throughout the day as they wish. Each PK visit requires that the participants take their morning dose of ruxolitinib and their ARV medications as observed doses administered in the clinic. Participants should be contacted the night before and reminded not to take their morning dose of ruxolitinib or their ARV medications until instructed during their clinic visit, and to bring their study and ARV medications (including EFV) with them in the morning. The timing of the previous drug administration must be documented. If participant skipped previous day's medication for the weeks 1 and 4 visits or took ruxolitinib before arriving at clinic, then baseline PK sampling should not be drawn and an alternative visit should be scheduled to measure PK. The exact time (hour and minute) of administration of the observed dose of ruxolitinib and ARV must be recorded on the CRF, along with the exact time at which each blood sample was obtained. Samples will be collected at the following time points during each visit:

Hour	Activity
-0.5 – 0.0	Pre-dose (baseline) PK sample
0.0	Observed Administration of study drug and
	ARV medications; start clock; record
	administration time
1.0 – 1.5	PK sample
2.5 – 4.0	PK sample
4.0 - 6.0	Lunch
6.0 - 8.0	PK sample

The use of an intravenous (IV) catheter is optional depending on **participant** preference. Please refer to the LPC for sample collection, processing, storage and shipping information.

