6.0 CLINICAL AND LABORATORY EVALUATIONS

6.1 Schedule of Events

Evaluation	Screening Pro	Pre-Entry	Entry		(On-Study (W	Evaluati eeks)				
				1	2	4	5	10	12	Confirmation	Premature
Window	≤30 days before entry	≥24 hours after screening and ≤7 days before entry		± 3 days			± 7 days		of Virologic Failure	Treatment/Study Discontinuation Evals.	
Documentation of HIV-1	Х										
Medical History	Х		Х								
Medication History	Х		Х								
Complete Physical Examination		х									
Targeted Physical Examination	x		Х	х	Х	Х	х	х	х		Х
Clinical Assessments			Х	Х	Х	Х	Х	Х	Х		Х
Concomitant Medications	Х		Х	Х	Х	Х	Х	Х	Х		Х
Study Treatment Modifications	х		Х	х	Х	Х	х	Х	х		Х
ART Modifications	Х		Х	Х	Х	Х	Х	Х	Х		Х
Hematology	Х		Х	Х	Х	Х	Х	Х	Х		Х
Liver Function Tests	Х		Х	Х	Х	Х	Х	Х	Х		Х
Blood Chemistries	Х		Х	Х	Х	Х	Х	Х	Х		Х
Fasting Lipid Panel			Х				х				X (if prior to week 5)
Pregnancy Testing	Х		X1			If sus	spected				
Nadir CD4+ T cell Count			Х								
Documentation of Pre- ART CD4+ T cell Count			Х								
CD4+/CD8+	Х	X ²	Х		Х		Х		Х		Х

Evaluation	Screening Pre	Pre-Entry	Entry		(Dn-Study (Wo	Evaluati eeks)				
				1	2	4	5	10	12	Confirmation	Premature
Window	≤30 days before entry	≥24 hours after screening and ≤7 days before entry		± 3 days			± 7 days		of Virologic Failure	Treatment/Study Discontinuation Evals.	
Stored PBMCs for Other Immunologic Studies			Х				х		х		х
Stored Plasma Soluble Markers		Х	Х			Х	х		х		Х
Stored Plasma Soluble Marker:IL-6		Х	Х			Х	х	х	х		×
Documentation of Pre- ART HIV-1 RNA			Х								
Plasma HIV-1 RNA	Х		Х		Х		Х		Х	Х	Х
Stored Plasma HIV-1 RNA for Single Copy Assay			Х				х		х		Х
Stored PBMC Reservoir Assays			Х				х		х		Х
Stored Plasma/PBMC		Х	Х		Х		Х		Х		Х
Stored Oral Swabs for HHV		x	X	х	X	x	х	x	x		X
Plasma PK Collection for Arm A				х		х					X (if prior to week 4)
Medication Diary for Arm A (D=Distribute; C=Collect)			X (D)	X (C)	X (D)	X (C)					X (C) (if prior to week 4)
Adherence Assessment			Х	Х	Х	Х	Х	Х	Х		Х

¹Refer to section 6.2.2 for pregnancy testing at study entry. ²Only one CD4+/CD8+ is required if screening and pre-entry visits are combined.

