9.6 Analyses

9.6.1 Primary Analyses

A5336 FINAL Version 2.0 05/21/15

As this is a pilot study of biologic activity, our primary analysis of efficacy will be an as-treated analysis, limited to **participants** who meet all of the following conditions: (a) have data at baseline and week 5, (b) for the ruxolitinib arm, remain on study treatment through week 5 and miss no more than 6 doses cumulatively, (c) did not change ART, use prohibited medications, or have a virologic failure during this time period.

Changes from baseline to week 5 in plasma IL-6 (on log_{10} scale) will be summarized with the mean and a 90% confidence interval (CI) for the mean change in each treatment arm, and compared between arms with a t-test. The baseline value will be calculated as the geometric mean of pre-entry and entry, and the week 5 value as the geometric mean of weeks 4 and 5. If missing one of the pre-entry or entry values, then the available measure will be used as the baseline value, and similarly, if missing one of the week 4 or week 5 values, then the available measure will be used as the week 5 value.

Safety will be evaluated by estimating the proportion of participants in the ruxolitinib arm who experienceing the primary safety outcome measure 9.2.1.1. In addition, safety will be compared between the treatment arms via a one-sided Fisher's exact test at 5% alpha level, in terms of 9.2.1.1, but with this composite safety outcome modified to address the A5336 design where Arm B does not receive any study treatment. Specifically "discontinuation of ruxolitinib due to thrombocytopenia" will be modified to "occurrence of Grade 2 or higher thrombocytopenia" and "any Grade 4 or recurrence of Grade 3 toxicity related to study drug" will be modified to "any Grade 4 or recurrence of Grade 3 toxicity." Tolerability will be evaluated by summarizing treatment modifications and discontinuations.

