### 3 General Analysis Considerations

Study entry is defined as the date of the entry visit recorded on study initiation case report form.

The protocol-defined study week windows are modified for analysis purposes. For all analyses, the following window definitions will be used:

Pre-entry:	The last visit that occurred at least 24 hours prior to entry, but not more than 7 days before
Entry:	The visit after randomization, and prior to initiation of study treatment: Days [0-3]
Week 1:	The first visit in the window: Days [4, 22]
Week 2:	The second visit in the window: Days [4, 22]
Week 4:	The first visit in the window: Days [25, 39]
Week 5:	The second visit in the window: Days [25, 39]
Week 10:	The first visit in the window: Days [56, 93]
Week 12:	The second visit in the window: Days [56, 93]

Baseline values are the average of pre-entry and entry values, the week 4/5 values are the average of week 4 and week 5 values, and the week 10/12 values are the average of week 10

and 12 values; averages will be calculated using geometric means for log-transformed data and arithmetic mean for non-transformed data. If missing one of the pre-entry or entry values, then the available measure will be used as the baseline value, and similarly, if missing one of the week 4 or week 5 values or week 10 or week 12 values, then the available measure will be used as the week 4/5 value or week 10/12 value, respectively.

Analyses will be done among those in the as-treated population or among those in the safety analysis population (Cameron 2008), depending on the outcome; see the Statistical Methods section for details on populations for specific outcomes. The safety analysis population will consist of all participants randomized to the no-treatment arm and all participants who took at least one dose of ruxolitinib among those randomized to the ruxolitinib arm. The as-treated population is defined as participants who meet the following conditions: (1) have data at baseline and week 4/5, (2) for the ruxolitinib arm, remained on study treatment through week 4/5 and missed no more than 6 doses cumulatively, (3) did not change ART, use prohibited medications, or had confirmed virologic failure in this time period. Participants found to be ineligible after enrollment will be included in all safety analyses, but excluded from other analyses.

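### At week 4, half of the primary on-treatment IL-6 value, only Arm A must attend fasted, which could bias the arm comparison by an unknown amount in either direction

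*Protocol*

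**What the plan says.** The Schedule of Events (Protocol 6.1) has IL-6 plasma collected at week 4 in both arms. The row "Plasma PK Collection for Arm A" in the same table is marked at weeks 1 and 4.

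Three rules bear on how the week 4 sample is taken:

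- **General fasting rule (Protocol 6.3.9).** "All laboratory evaluations at entry and week 5 study visit must be collected in a fasting state". The fast is 8 hours, and non-fasting participants are recalled within 72 hours. Week 4 and pre-entry are not listed.
- **PK visits, Arm A only (Protocol 6.3.22).** "Apart from arriving at the clinic in a fasted state", participants are free to eat and drink during the day. The morning ruxolitinib and antiretroviral doses are taken under observation in the clinic, and the last PK sample falls 6 to 8 hours after dosing. Collection details are left to the Laboratory Processing Chart, which is not among the documents.
- **Time of day (Protocol 6.3.12).** The section opens its rule with "Because of the diurnal variation in biomarkers that may be measured as part of the study" and asks that each participant's draws stay in the same half of the day, where this can be managed. It does not mention fasting.

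Protocol 9.6.1 defines "the week 5 value as the geometric mean of weeks 4 and 5". SAP section 3 keeps this and adds that "if missing one of the week 4 or week 5 values", the available one stands alone.

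**The concern.** Week 4 carries half the weight of the on-treatment value when both samples exist, and all of it when week 5 is missing. At that visit the written collection conditions depend on the arm. The difference arises after randomisation and because of the allocation, so randomisation does not balance it, and the planned t-test does not adjust for it.

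If fasting shifts plasma IL-6, part of that shift would be counted as treatment effect. It could imitate a drug effect or hide one. The protocol controls fasting in both arms at entry and week 5, but not at the other visit in the on-treatment value.

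**Working it through.** **Inputs from Protocol 9.4.1.** Design difference 0.20 log10 pg/mL; SD of within-participant change 0.25; two-sided alpha 0.10; 2:1 allocation; 48 evaluable participants, hence 32 and 16.

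**Assumed input.** The documents give no fasting effect on IL-6. I take a week 4 difference between arms of b = 0.05 to 0.10 log10. Since 10^0.05 = 1.12 and 10^0.10 = 1.26, this is a 12% to 26% difference in that one sample.

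**The plan's own figure.**

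- SE = 0.25 × √(1/32 + 1/16) = 0.0765.
- Non-centrality = 0.20 / 0.0765 = 2.61, with 46 degrees of freedom and critical value 1.679.
- Power = 82.4%. With the unrounded average SD, (0.2448 + 0.2648)/2 = 0.2548, power = 81.1%.

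The stated 80% is reproduced, slightly on the cautious side.

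**Bias in the contrast.** On the log10 scale a geometric mean of two samples is their simple average, so a week 4 shift enters at half its size: bias = b/2.

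- b = 0.05: bias 0.025, which is 0.025/0.20 = 12.5% of the design difference.
- b = 0.10: bias 0.05, which is 25% of the design difference.

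**Consequences at SD 0.25, 32 versus 16 (non-central t).** The full case takes all Arm A week 4 samples as fasted and all Arm B samples as unfasted. In the half case only half of Arm B is unfasted, so the mean bias is b/4; the small extra variance is ignored.

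| | b = 0.05 | b = 0.10 |
|---|---|---|
| Type I error, full case (nominal 10%) | 11.8% | 16.9% |
| Power if the shift opposes the drug, full case (82.4% without bias) | 72.8% | 61.3% |
| Type I error, half case | 10.4% | 11.8% |

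**Baseline.** Entry is fasted in both arms. Pre-entry precedes randomisation, so its lack of a fasting rule cannot create a difference between arms.

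**Power of a week 5 analysis.** The SD of 0.25 claims no gain from averaging two samples: Protocol 9.4.1 states that one source SD rests on a single measure, and the correlation of 0.68 is between single time points. On the plan's own SD, a comparison using week 5 alone should keep about the planned power.

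**The case against.** A reader might infer that the week 4 IL-6 sample is drawn fasted in Arm A. The documents do not say so. Arm A must arrive fasted, may then eat, and stays for up to 8 hours after dosing. No section gives the time of the IL-6 tube. Section 6.3.22 also allows PK sampling to move to another visit in some cases, so the PK and IL-6 draws need not coincide. This objection stands. It also shows that the draw time is open.

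A reader might also infer that a bias has been shown. It has not: nothing in the documents says that fasting changes IL-6, or in which direction, and nothing stops Arm B participants from fasting.

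Time of day is a weaker argument than it looks. Section 6.3.12 keeps each participant in the same half-day, and the endpoint is a within-participant change, so a stable time-of-day effect largely cancels. What remains is departures from a rule that applies only where feasible.

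Finally, a separate week 5 comparison may already be intended. Protocol 9.2.2.3 lists IL-6 change to week 5 apart from week 4, and SAP 4.2.3 compares arms at each post-entry week. But SAP 4.2.3 also averages weeks 4 and 5, and its baseline averages pre-entry with entry. The SAP does not clearly commit to an analysis in which every sample is fasted in both arms.

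**Conclusion.** The point holds as a gap in the collection rules. At week 4 the fasting requirement applies to Arm A and not to Arm B, and week 4 is half of the primary on-treatment value. The resulting bias is possible, with unknown size and direction.

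The range in the working depends on an assumed shift of 0.05 to 0.10 log10 and, at its worst, on complete separation of the arms by fasting status. With half of Arm B unfasted, the lower end of the range is close to nominal. The documents do not support the stronger reading that the IL-6 comparison is biased. Severity is minor; the case for acting is that the remedy costs little.

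**What to change.** **Protocol 6.3.9.** Extend the 8-hour fast to the week 4 soluble-marker and IL-6 draw in both arms. State that this tube is drawn on arrival, while the participant is still fasted; in Arm A, take it with the pre-dose PK sample. Record fasting status in both arms.

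**SAP.** Add a supportive between-arm analysis of IL-6 change from entry to week 5 alone, where the protocol already requires fasting in both arms. Agreement with the primary result would be reassuring; a clear difference would point to week 4.

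**Cost.** Arm B participants fast before one existing visit, and no visit is added. The supportive analysis uses samples already scheduled and can be specified even if the week 4 samples have been taken.
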